6.1. Demographics, Baseline Characteristics, and Disease History

Demographics, baseline characteristics, and disease history will be summarized by treatment group and overall.

6.1.1. Demographics and Baseline Characteristics

The following demographics will be summarized for the ITT population and the extension evaluable population: age, sex, race, ethnicity, weight, height, BMI, and BMI category (< 25 kg/m², \ge 25 to < 30 kg/m², \ge 30 to < 40 kg/m², \ge 40 to < 50 kg/m², \ge 50 kg/m²).

The following demographics will be summarized for the ITT population only: tobacco use (never used, current user, former user).

6.1.2. Baseline Disease Characteristics and Disease History

The baseline disease characteristics and disease history summarized for all participants in the ITT population include but are not limited to the following:

- Disease duration (years)
- Fitzpatrick scale skin type (Type I, II, III, IV, V, VI)
- Vitiligo family history
- Prior therapy or surgery for vitiligo treatment
- Selected comorbidities
- Baseline F-BSA involvement
- Baseline F-BSA involvement category (≤ 0.5%, > 0.5%-1.0%, > 1.0%-1.5%, > 1.5%-2.0%, > 2.0%-2.5%, > 2.5%-3.0%)

- Baseline T-BSA involvement
- Baseline T-BSA involvement category (≤ 8.0%, > 8.0%-14.0%, > 14.0%-20.0%, > 20.0%-30.0%, > 30.0%-40.0%, > 40.0%-50.0%, > 50.0%-80.0%, > 80.0%)
- Baseline T-BSA involvement stratification category (8.0%-20.0%, > 20.0%)
- Baseline T-VASI score
- Baseline T-VASI score category (≤ 8.0, > 8.0-14.0, > 14.0-20.0, > 20.0-30.0, > 30.0-40.0, > 40.0-50.0, > 50.0-80.0, > 80.0)
- History of acne vulgaris (no/yes)
 Currently having acne vulgaris (no/yes)
 Vitiligo in genital area (no/yes)

Note: disease duration (years) will be calculated as follows:

disease duration (years) = (date of randomization – date of diagnosis + 1) / 365.25.

6.1.3. Medical History

For participants in the ITT population, medical history will be summarized by assigned treatment group. This summary will include the number and percentage of participants with medical history for each body system/organ class as documented in the eCRF.

6.2. Disposition of Participant

The number of participants enrolled by country and/or site will be summarized for the ITT population by treatment group and overall.

The following will be summarized by treatment group and overall for the ITT population in the PC period:

- Number (%) of participants who were randomized
- Number (%) of participants who were treated in the PC period
- Number (%) of participants who completed treatment in the PC period through Week 24
- Number (%) of participants who discontinued study treatment in the PC period with a primary reason for discontinuation
- Number (%) of participants who withdrew from the study in the PC period with a primary reason for withdrawal

The following will be summarized by treatment group and overall for the extension evaluable population in the extension period:

- Number (%) of participants who were treated in the extension period
- Number (%) of participants who completed treatment in the extension period
- Number (%) of participants who discontinued study treatment in the extension period with a primary reason for discontinuation
- Number (%) of participants who completed the study
- Number (%) of participants who withdrew from the study in the extension period with a primary reason for withdrawal

6.3. **Protocol Deviations**

Protocol deviations recorded will be summarized by treatment group and overall, for the ITT population in the PC period and the extension evaluable population in the extension period, and listed.

6.4. Exposure

For participants in the safety population in the PC period, the extension evaluable population in the extension period, and those who took INCB054707 45 mg or 75 mg throughout study participation, study drug exposure will be summarized by treatment group descriptively as the following:

• **Duration of treatment with study drug (days)**: date of last dose of study drug in the specific period – date of first dose of study drug in the specific period + 1.

The date of first and last doses of study drug in each period are defined in Table 3.

Treatment Period	Treatment Group	First Dose Date	Last Dose Date
PC period	Placebo INCB054707 15 mg INCB054707 45 mg INCB054707 75 mg	Date that the first dose of study drug was administered to the participants in the PC period	Date that the last dose of study drug was administered to the participants in the PC period
Extension period	Placebo to INCB054707 75 mg INCB054707 15 mg to 75 mg INCB054707 45 mg INCB054707 75 mg	Date that the first dose of study drug was administered to the participants in the extension period	Date that the last dose of study drug was administered to the participants in the extension period
Throughout study participation	INCB054707 45 mg INCB054707 75 mg	Date that the first dose of study drug was administered to the participants in the PC period	Date that the last dose of study drug was administered to the participants throughout study participation

Table 3:	Definition	of First	and Las	t Dose Date

In addition, for the safety population in the PC period and the extension evaluable population in the extension period, average daily dose of INCB054707 and total actual dose of INCB054707 will be summarized by treatment group descriptively as follows:

- Average daily dose of INCB054707 (mg/day): total actual INCB054707 dose taken in the specific period (mg) / [duration of treatment with INCB054707 in the specific period (days) number of interrupted days with INCB054707 in the specific period].
- Total actual dose of INCB054707 taken (mg): (total number of tablets dispensed in the specific period total number of tablets returned in the specific period) × 15 (mg/tablet) × p_T

in which p_T denotes the proportion of INCB054707 among the 5 tablets taken daily with $p_T = 0$ (0/5) for the placebo group, 1/5 for the INCB054707 15 mg group, 3/5 for the INCB054707 45 mg group, and 1 (5/5) for the INCB054707 75 mg group.

The total number of tablets dispensed and returned in each period is based on information entered in the Drug Accountability eCRF. If there is dispensed drug that has not been returned, the actual dose taken starting from the dispense date of the unreturned drug will be imputed by the dose taken as reported in the Compliance eCRF.

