5. STATISTICAL METHODOLOGY

5.1. General Methodology

Unless otherwise noted, SAS[®] software (SAS Institute Inc, Cary, NC; v9.1 or later) will be used for the generation of all tables, graphs, and statistical analyses. Descriptive summaries for continuous variables will include but not be limited to the number of observations, mean, standard deviation, median, minimum, and maximum. Descriptive summaries for categorical variables will include the number and percentage of participants in each category.

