5.3.4. Extension Evaluable Population

All analyses for the extension period will be conducted with the extension evaluable population, which includes all participants who received at least 1 dose of INCB054707 during the extension period.

6. **BASELINE, EXPOSURE, AND DISPOSITION**

Appendix A provides a list of data displays. Sample data displays are included in a separate document.

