6.5. Study Drug Compliance

For participants in the safety population and the extension evaluable population, the overall compliance (%) for INCB054707/placebo will be calculated for all participants as follows:

compliance (%) = $100 \times$ [total dose actually taken in the specific period] / [total prescribed dose in the specific period].

The total prescribed dose in the specific period is defined as the sum of the doses prescribed by the investigator accounting for dose interruptions during the specific period, and will be calculated as: [duration of treatment with study drug in the specific period – number of days with dose interruptions in the specific period] \times 5 (tablets/day).

The total dose actually taken in the specific period will be calculated as: total number of tablets dispensed in the specific period – total number of tablets returned in the specific period (see Section 6.4 for details on total number of tablets dispensed and returned).

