8.2.2. Adverse Event Summaries

Adverse events will be summarized by treatment group and overall INCB054707 dose groups for the safety population in the PC period. For the extension evaluable population in the extension

period and for participants who took INCB054707 45 mg or 75 mg throughout study participation, AEs will be summarized by treatment group and overall.

An overall summary of AEs will include the following:

- Number (%) of participants reporting any TEAEs
- Number (%) of participants reporting any serious TEAEs
- Number (%) of participants reporting any Grade 3 or higher TEAEs
- Number (%) of participants reporting any treatment-related TEAEs
- Number (%) of participants who temporarily interrupted study treatment because of TEAEs
- Number (%) of participants who permanently discontinued study treatment because of TEAEs
- Number (%) of participants who had a fatal TEAE

The following summaries will be produced by MedDRA term (if 10 or fewer participants appear in a table, a listing may be appropriate):

- Summary of TEAEs by MedDRA SOC and PT
- Summary of TEAEs by MedDRA PT in decreasing order of frequency
- Summary of TEAEs by MedDRA SOC, PT, and maximum severity
- Summary of TEAEs by MedDRA SOC, PT, and CTCAE grade category
- Summary of Grade 3 or higher TEAEs by MedDRA SOC and PT
- Summary of Grade 3 or higher TEAEs by MedDRA PT in decreasing order of frequency
- Summary of serious TEAEs by MedDRA SOC and PT
- Summary of serious TEAEs by MedDRA PT in decreasing order of frequency
- Summary of treatment-related TEAEs by MedDRA SOC and PT
- Summary of treatment-related TEAEs by MedDRA PT in decreasing order of frequency
- Summary of Grade 3 or higher treatment-related TEAEs by MedDRA SOC and PT
- Summary of treatment-related serious TEAEs by MedDRA SOC and PT
- Summary of TEAEs with a fatal outcome by MedDRA SOC and PT
- Summary of TEAEs leading to dose interruption by MedDRA SOC and PT
- Summary of TEAEs leading to discontinuation of study drug by MedDRA SOC and PT
- Summary of TEAEs requiring concomitant medications by MedDRA SOC and PT

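### Does the SAP's average daily dose hide dose lost to interruptions because interrupted days are taken out of its denominator?

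*SAP*

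**What the plan says.** SAP 6.4 (Exposure) defines three descriptive measures for each study period.

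- **Duration of treatment:** last dose date minus first dose date, plus 1.
- **Total actual dose:** tablets dispensed minus tablets returned, times 15 mg, times p_T, the share of active tablets among the 5 taken daily. p_T is 0, 1/5, 3/5 and 1 for placebo, 15, 45 and 75 mg.
- **Average daily dose:** total actual dose divided by duration less the "number of interrupted days with INCB054707 in the specific period".

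For the last two, the section states that "average daily dose of INCB054707 and total actual dose of INCB054707 will be summarized by treatment group descriptively". SAP 5.1 says that descriptive summaries of continuous variables include at least "the number of observations, mean, standard deviation, median, minimum, and maximum".

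SAP 6.5 (Study Drug Compliance) divides tablets taken by the prescribed number, described as "accounting for dose interruptions during the specific period". The prescribed number is duration less the "number of days with dose interruptions in the specific period", times 5 tablets a day. For the tablet counts, 6.5 refers back to 6.4.

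SAP 8.2.2 counts interruptions caused by adverse events in two ways: "Number (%) of participants who temporarily interrupted study treatment because of TEAEs" and "Summary of TEAEs leading to dose interruption by MedDRA SOC and PT". SAP section 6 opens by pointing to a list of displays in Appendix A and adds: "Sample data displays are included in a separate document".

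**The concern.** Protocol 6.5 allows no dose modification, but it does allow temporary interruption for adverse events or laboratory abnormalities. Interruption is thus the protocol's own route by which intake falls below the planned dose. A row called average daily dose that leaves those days out could be read as intake over the whole treatment period, which it is not. The row also appears to add nothing, because it rescales the compliance row.

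Protocol 2.2.1 says the study is meant to inform the choice of dose for a possible Phase 3 study, and interruptions could differ between arms. Protocol 2.3.1 reports platelet decreases at 60 mg QD and above with a dose-related trend, and interruptions of up to 2 weeks in 4 of 8 hidradenitis suppurativa participants at 90 mg. If interruptions were more frequent at 75 mg than at 15 mg, the row would not show the difference. At stake is an accurate account of the dose each arm received.

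**Working it through.** **Inputs.** T = tablets dispensed minus returned (SAP 6.4, used again in 6.5). D = duration in days (6.4). I = interrupted days (6.4 and 6.5). Tablets are 15 mg, 5 a day, with active share p_T (6.4). The placebo-controlled period is nominally 24 weeks = 168 days (SAP 3). The minus sign before I is missing from the extracted text of 6.4; it is read from the parallel expression in 6.5.

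**Group doses reproduced.** 5 × 15 × p_T = 0, 15, 45 and 75 mg/day.

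**The identity.**

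- Average daily dose = T × 15 × p_T / (D − I)
- Compliance = 100 × T / [(D − I) × 5]
- Hence average daily dose = (compliance/100) × 75 × p_T

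A check with exact fractions on 100,000 random sets of group, D, I and T gave no mismatch.

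**One 75 mg participant, D = 168.** The first three rows assume every tablet is taken on non-interrupted days.

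| I (days) | T | Total (mg) | Compliance | SAP average daily dose | Total / D |
|---|---|---|---|---|---|
| 0 | 840 | 12,600 | 100% | 12,600/168 = 75.0 | 75.0 |
| 7 | 805 | 12,075 | 100% | 12,075/161 = 75.0 | 71.9 (−4.2%) |
| 14 | 770 | 11,550 | 100% | 11,550/154 = 75.0 | 68.75 (−8.3%) |
| 14, 90% of tablets taken | 693 | 10,395 | 90% | 10,395/154 = 67.5 | 61.9 |

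The average daily dose responds to missed tablets but, at given adherence, not to interrupted days. The total-dose column does respond: it falls by 1,050 mg (14 × 75) with a 14-day interruption. That column is itself a planned participant-level summary.

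**Arm level.** Suppose 10%, 25% or 50% of the 75 mg arm has a 14-day interruption and all have D = 168. The shares are assumptions, since the documents give no interruption rate at 15, 45 or 75 mg.

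| Share | Mean total: 12,600 − share × 1,050 (mg) | Mean total / 168 (mg/day) | Shortfall from 75 |
|---|---|---|---|
| 10% | 12,495 | 74.4 | 0.6 (0.8%) |
| 25% | 12,337.5 | 73.4 | 1.6 (2.1%) |
| 50% | 12,075 | 71.9 | 3.1 (4.2%) |

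Each figure is a planned mean total dose divided by a planned mean duration, so the dose delivered to the arm can be obtained from the planned tables. The shortfall compares with 30 mg between adjacent active doses.

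**Where the planned means fall short.** Take an invented pair in the 75 mg arm: one with D = 168 and I = 0 (12,600 mg), one with D = 56 and I = 14 (42 × 75 = 3,150 mg). Ratio of means = 15,750/224 = 70.3. Participant ratios are 75.0 and 56.25, with mean 65.6. The SAP row shows 75.0 for both. With unequal durations, the ratio of arm means and the mean of participant ratios differ.

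**The case for a change.** The best case for changing the SAP runs as follows. The row's name does not say that interrupted days are excluded. Within an active group it repeats the compliance row. No visible summary gives each participant's dose over the full duration, or the number of days interrupted; section 8.2.2 counts participants and events, not days. A ratio of arm means weights by duration and has no spread of its own. All the inputs are already collected, so a clearer label and one or two rows would cost very little.

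The observations stand; the conclusion that something is wrong does not follow from them.

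- **The definition is open.** Section 6.4 prints the denominator, and 6.5 uses the same convention and says so. Nobody applying the formula would compute a wrong number.
- **The lost dose is not hidden.** Total actual dose is summarized across participants with mean, standard deviation, median, minimum and maximum, and duration is also summarized descriptively. With a common planned 24 weeks, the two together show most of what a further row would.
- **The remaining gap is narrow.** It is the distribution of one participant-level ratio and a count of days. Either may already be in Appendix A or the sample displays, which are not available here.
- **The proposed row has its own blind spot.** Its denominator ends at the last dose, so an interruption never followed by a restart falls outside it too.
- **The link to dose selection is thin.** Efficacy in the placebo-controlled period is analyzed by randomized group (SAP 5.3.2), whatever this row shows.

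**Conclusion.** The concern does not hold. The algebra is right: average daily dose in SAP 6.4 is compliance times the group's dose and, at given adherence, does not move with interrupted days. But this is the stated and legitimate meaning of an average over non-interrupted days, not an arithmetic error, and following the plan as written gives no wrong result. The total-dose and duration summaries in the same section carry the dose lost to interruptions.

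The difference in question is 8.3% for an otherwise adherent participant with 14 of 168 days off. For a 75 mg arm it is 0.8% to 4.2% under assumed shares of 10% to 50%. The 14 days are the maximum reported at 90 mg in another indication, a dose not used here. The difference touches descriptive exposure reporting only; no visible test, estimate, decision rule or conclusion depends on it.

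The identity rests on three readings: that the minus sign in 6.4 was lost in extraction; that the interrupted days in 6.4 and 6.5 are the same count; and that the imputation for unreturned drug in 6.4 feeds both formulas, as the cross-reference in 6.5 implies. It holds for any p_T, so it also covers the extension groups that switch to 75 mg, for which 6.4 names no p_T. If any of these readings failed, the row would no longer merely repeat compliance, and the case against it would be weaker still.

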6.5. Study Drug Compliance

For participants in the safety population and the extension evaluable population, the overall compliance (%) for INCB054707/placebo will be calculated for all participants as follows:

compliance (%) = $100 \times$ [total dose actually taken in the specific period] / [total prescribed dose in the specific period].

The total prescribed dose in the specific period is defined as the sum of the doses prescribed by the investigator accounting for dose interruptions during the specific period, and will be calculated as: [duration of treatment with study drug in the specific period – number of days with dose interruptions in the specific period] \times 5 (tablets/day).

The total dose actually taken in the specific period will be calculated as: total number of tablets dispensed in the specific period – total number of tablets returned in the specific period (see Section 6.4 for details on total number of tablets dispensed and returned).

6.6. Prior and Concomitant Medication

Prior medications and concomitant medications will be coded using the WHO Drug Dictionary. For the ITT population in the PC period, both prior and concomitant medications will be summarized by treatment group and overall. For the extension evaluable population in the extension period, only concomitant medication will be summarized by treatment group and overall. All summaries will be by WHO drug class and WHO drug preferred term.

7. EFFICACY

Appendix A provides a list of data displays. Sample data displays are included in a separate document.

7.1. General Considerations

All by-visit analyses for the extension evaluable population will include the follow-up period if the data are available, unless otherwise specified.

Unless otherwise stated, the strata identified in the randomization process will be used in all efficacy analyses.

Total body VASI (T-VASI) is calculated using a formula that includes contributions from all body regions (possible range: 0-100) as follows:

VASI = $\sum_{\text{all body sites}} [\text{Hand Units}] \times [\text{Residual Depigmentation}]$

The body is divided into the following 6 separate and mutually exclusive sites: (1) head/neck, (2) hands, (3) upper extremities (excluding hands), (4) trunk, (5) lower extremities (excluding feet), and (6) feet. The percentage of vitiligo involvement is estimated in hand units (%BSA) by the same investigator during the entire course of the study. Hand unit is based on the participant's hand size. The investigator uses their hand to mimic the participant's hand size to evaluate %BSA vitiligo involvement. The degree of depigmentation for each body site is determined and estimated to the nearest of the following percentages: 0%, 10%, 25%, 50%, 75%, 90%, or 100%. The T-VASI is then derived by multiplying the values assessed for the vitiligo involvement by the percentage of affected skin for each body site and summing the values of all body sites together (Hamzavi et al 2004).

The T-VASI50 is defined as at least 50% reduction from baseline in T-VASI.

7.3. Efficacy Hypotheses

The primary hypothesis is that INCB054707 75 mg is superior to placebo at Week 24 in mean percent change from baseline in T-VASI in participants with vitiligo. Assuming μ_T is the mean percent change from baseline at Week 24 in T-VASI in the INCB054707 75 mg group and μ_C is the mean percent change from baseline at Week 24 in T-VASI in the placebo group, the primary hypotheses of the study are as follows:

- H_0 (null hypothesis): $\mu_T = \mu_C$
- H_A (alternative hypothesis): $\mu_T \neq \mu_C$

7.4. Analysis of the Primary Efficacy Parameter

The primary efficacy endpoint is the percent change from baseline in T-VASI at Week 24.

7.4.1. Primary Efficacy Analysis

7.4.2. Subgroup Analyses for Primary Endpoint

A subgroup will be formed based on the following participant characteristics and baseline variables for those participants whose data are available:

• Baseline T-BSA involvement (8.0%-20.0%, > 20.0%)

The primary efficacy endpoint will be summarized using descriptive statistics based on the ITT population for the subgroups defined above.

7.4.3. Sensitivity and Supportive Analyses for Primary Endpoint

Not applicable.

7.5. Analysis of the Secondary Efficacy Parameters

The key secondary efficacy endpoint is proportion of participants who achieve T-VASI50 at Week 24.

8. SAFETY AND TOLERABILITY

Appendix A provides a list of data displays. Sample data displays are included in a separate document.

8.1. General Considerations

The analyses in this section will be provided for the safety population in the PC period and the extension evaluable population in the extension period unless otherwise specified. Summary tables may be replaced with listings when appropriate. For instance, an AE frequency table may be replaced with a listing if it only contains a few unique PTs reported on relatively few participants.

8.2. Adverse Events

8.2.1. Adverse Event Definitions

A TEAE is any AE either reported for the first time or worsening of a pre-existing event after the first dose of study drug until the end of the safety follow-up.

A TEAE in the PC period is any AE with a start time after the first dose of study drug in the PC period and until the end of the safety follow-up, or prior to the first dose in the extension period for participants who entered in to the extension period.

A TEAE in the extension period is any AE with a start time after the first dose of study drug in the extension period until the end of the safety follow-up.

For participants who took INCB054707 45 mg or 75 mg throughout study participation, a TEAE is any AE with a start time after the first dose of study drug in the PC period until the end of the safety follow-up.

Analysis of AEs (as discussed below) will be limited to TEAEs, but data listings will include all AEs regardless of their timing in relation to study drug administration. For purposes of analysis, all AEs will be considered TEAEs unless the AE can unequivocally be defined as not treatment-emergent.

Adverse events will be tabulated by MedDRA PT and SOC. Severity of AEs will be graded using the NCI CTCAE v5.0. The CTCAE reporting guidelines and grading details are available on the Cancer Therapy Evaluation Program website.

The subset of AEs considered by the investigator to be related to study drug will be considered to be treatment-related AEs. If the investigator does not specify the relationship of the AE to study drug, the AE will be considered to be treatment-related. The incidence of AEs and treatment-related AEs will be tabulated. In addition, serious TEAEs will also be tabulated.

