 - There may be situations in which an SAE has occurred and the investigator has minimal information to include in the initial report. However, the causality assessment is one of the criteria used when determining regulatory reporting requirements. **Therefore, it is very important that the investigator always make an assessment of causality based on the available information for every event before the initial transmission of the SAE.**
 - The investigator may change his/her opinion of causality in light of follow-up information and submit the updated causality assessment.

Follow-Up of Adverse Events and Serious Adverse Events

- The investigator is obligated to perform or arrange for the conduct of supplemental measurements and/or evaluations as medically indicated or as requested by the sponsor to elucidate the nature and/or causality of the AE or SAE as fully as possible. This may include additional laboratory tests or investigations, histopathological examinations, or consultation with other health care professionals.
- Once an AE is detected, it should be followed in the AE eCRFs until it has resolved or until it is judged to be permanent; assessment should be made at each visit (or more frequently if necessary) of any changes in severity, the suspected relationship to the study drug, the interventions required to treat the event, and the outcome.
- When the severity of an AE changes over time for a reporting period (eg, between visits), each change in severity will be reported as a separate AE.
- If a participant dies during participation in the study or during a recognized follow-up period, the investigator will provide the sponsor with a copy of any postmortem findings, including histopathology.
- Updated SAE information will be recorded in the originally completed eCRF and reported to Incyte Pharmacovigilance (either via email/fax if paper SAE form is used or in the SAE EDC CRF) until resolution, stabilization, the event is otherwise explained, or the participant is lost to follow-up.
- Any updated SAE data (including SAEs being downgraded to nonserious) will be submitted to the sponsor (or designee) within 24 hours of receipt of the information.

See [Appendix D](#) for the management of potential Hy's Law cases.

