- Follow-up information is also recorded in the eCRF and transmitted to Incyte Pharmacovigilance via the EDC system. The follow-up report should include information that was not provided previously, such as the outcome of the event, treatment provided, action taken with study drug because of the SAE (eg, dose reduced, interrupted, or discontinued), or participant disposition (eg, continued or withdrew from study participation). Each recurrence, complication, or progression of the original event should be reported as follow-up to that event, regardless of when it occurs.

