10.4.3. Safety Analyses

Safety analyses will be conducted for the safety population. A TEAE is any AE either reported for the first time or worsening of a pre-existing event after the first dose of study drug until the end of the safety follow-up period. Analysis of AEs will be limited to TEAEs, but data listings will include all AEs regardless of their timing to study drug administration. Adverse events will be tabulated by the MedDRA preferred term and system organ class. Severity of AEs will be based on the National Cancer Institute CTCAE v5.0 using Grades 1 through 5.

The subset of AEs considered by the investigator to have a relationship to study drug will be considered to be treatment-related AEs. If the investigator does not specify the relationship of the AE to study drug, then the AE will be considered treatment-related. The incidence of AEs and treatment-related AEs will be tabulated.

The clinical laboratory data will be analyzed using summary statistics; no formal treatment group comparisons are planned. Laboratory test values outside the normal range will be assessed for severity based on the normal ranges for the clinical reference laboratory. The incidence of abnormal laboratory values and shift tables relative to baseline will be tabulated. Descriptive statistics and mean change from baseline will be determined for vital signs (blood pressure, pulse, respiratory rate, and body temperature) at each assessment time. Descriptive statistics and mean change from baseline will be determined for each ECG parameter at each assessment time.

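### SAP 8.2.1 assigns adverse events to a study period by start time alone, so some events crossing into the extension can appear in the wrong column (minor, cheap to fix)

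*SAP*

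**What the plan says.** SAP 8.2.1 opens with a general definition: "A TEAE is any AE either reported for the first time or worsening of a pre-existing event after the first dose of study drug". Protocol 10.4.3 has the same two limbs, a first report or "worsening of a pre-existing event after the first dose of study drug until the end of the safety follow-up period". It gives no rule for separate periods.

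The SAP then adds period rules:

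- PC period: "A TEAE in the PC period is any AE with a start time after the first dose of study drug in the PC period", closed at the first extension dose for those who continue.
- Extension: "A TEAE in the extension period is any AE with a start time after the first dose of study drug in the extension period".
- Participants on 45 mg or 75 mg throughout: the same form, counted from the first PC dose.

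A default follows: "all AEs will be considered TEAEs unless the AE can unequivocally be defined as not treatment-emergent".

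The Protocol determines what records exist. Under Protocol 9.3, when severity "changes over time for a reporting period (eg, between visits), each change in severity will be reported as a separate AE". For serious events the same section says "Updated SAE information will be recorded in the originally completed eCRF", and Protocol 9.4 adds "Each recurrence, complication, or progression of the original event should be reported as follow-up to that event, regardless of when it occurs".

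For measurements, SAP 4.1.3 resets the safety baseline at the first extension dose. SAP 5.2 presents the two periods separately. Its extension groups include placebo to 75 mg and 15 mg to 75 mg.

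**The concern.** Participants from the placebo and 15 mg arms change treatment at the period boundary, so the period to which an AE is assigned decides the treatment it is shown under. The general definition asks for onset or worsening, but its only reference point is the first dose of study drug in the whole study. The period rules move the reference point to each period's first dose and keep only the date. No sentence asks whether an event already ongoing at the first extension dose got worse after it.

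At stake are the extension TEAE tables for the groups that switch treatment and, for serious events, the severity tables of the PC period. A reader could see an event under a dose on which it neither began nor worsened, or fail to see a worsening under the dose on which it happened.

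**Working it through.** **Step 1: classify events at the boundary.** The plan gives no figure to reproduce. The table compares a condition anchored at the first extension dose (first occurrence, or a rise in grade) with the start-time rule as written, for an AE that could appear in the extension.

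| Event | Anchored condition | Start-time rule with the Protocol's records |
|---|---|---|
| Non-serious, new in the extension | counts | counts |
| Non-serious, PC onset, unchanged | does not count | does not count |
| Non-serious, PC onset, worsens | counts | counts, if the separate record is dated at the change |
| Non-serious, PC onset, only improves | does not count | counts, if decreases are recorded and dated at the change |
| Serious, PC onset, worsens | counts | does not count, if the single record keeps its PC start date |

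The last two rows disagree.

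*Improving non-serious AE.* Protocol 9.3 refers to each change in severity, which literally includes a decrease. The general recording trigger in the same section is an AE that begins or worsens, so practice may differ. Each AE must have a start date, but neither document says which one a severity-change record carries. The eCRF completion guidelines mentioned in Protocol 11.2 may settle this; they were not available.

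*Worsening SAE.* Updates and progression stay with the original event. If its start date is unchanged, the event fails the extension rule and meets the PC rule, now carrying the grade reached in the extension. The severity-change instruction in Protocol 9.3 is worded for AEs generally. If sites also open a separate, newly dated record for an SAE, this route closes.

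**Step 2: size per affected participant.** SAP 8.2.2 counts participants, so one person changes a row by 1/n, and only if that person has no other qualifying record in the row. SAP 3.1 gives about 40 per group and 160 in total. The shares not entering the extension are assumptions.

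| Not entering the extension | One extension group | All extension groups pooled |
|---|---|---|
| 0% | 1/40 = 2.5 points | 1/160 = 0.6 points |
| 10% | 1/36 = 2.8 points | 1/144 = 0.7 points |
| 20% | 1/32 = 3.1 points | 1/128 = 0.8 points |

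- Improving non-serious AE: the extension row is too high by this amount.
- Worsening SAE: the extension row is too low by this amount. The PC preferred-term row does not change, because the participant is already counted there. The PC row for Grade 3 or higher rises by 1/40 = 2.5 points only if the event reaches Grade 3 or higher in the extension and the participant has no other such record in that row.

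The documents give no AE frequencies for this population, so the number of affected participants cannot be derived.

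**The case against.** The strongest reply is that the SAP does not contradict itself. The opening definition has one anchor and assigns no period. An AE that began on PC treatment is already treatment-emergent, and the period sentences merely place its records by date. This stands. A reader might infer that the period rules break the opening definition whichever date a record carries. That follows only if the definition is re-anchored at each period's first dose. Re-anchoring is sensible and parallels the baseline reset in SAP 4.1.3, but the SAP does not adopt it for AEs.

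A reader might also infer that worsening of ordinary AEs is lost from the extension. For non-serious AEs the documents give little support for this. A change in severity is a separate AE, and nothing says the new record keeps the earlier onset date. The route by which a worsening is missed is better documented for SAEs.

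Two defences fail:

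- Letting the opening definition govern does not remove the improving case. Its anchor is the first dose of study drug, which includes placebo (SAP 4.1.1). An event that began on placebo already satisfies it, and its improved record can then meet the extension rule as well.
- The default rule decides whether an AE is treatment-emergent, not to which period it belongs.

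The objection on impact largely stands. Dose attribution changes only for the two switching groups. The extra record in the improving case carries a reduced grade, and listings show all AEs whatever their timing.

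**Conclusion.** The point holds as a minor, inexpensive improvement to the stated rule. Read literally, SAP 8.2.1 can place an improving non-serious AE under 75 mg although it began on placebo or 15 mg. It can also leave a worsening SAE out of the extension and show its higher grade in the PC column.

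The first result assumes that decreases are recorded and dated at the change. The second assumes that the SAE's single record keeps its PC start date. The documents confirm neither.

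The size is about 2.5 points in an extension row per affected participant, for an unknown and possibly zero number of participants. It would be wrong to conclude that the safety results are materially distorted: the tables are descriptive, the periods are not summed, and no efficacy result depends on the rule. The summary of participants on 45 mg or 75 mg throughout gains nobody from a PC-onset AE, because such a participant is already counted there.

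**What to change.** In SAP 8.2.1:

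- Define a TEAE of a period as an event that first occurs after that period's first dose, or one whose CTCAE grade rises above its grade at that first dose. A record showing only a decrease in an event ongoing at that dose then does not qualify.
- Apply the same rule to SAE follow-up, using the date of worsening rather than the original onset.
- Keep every in-period record of a qualifying event, so that dose-interruption and discontinuation flags are not lost.
- State which start date a severity-change record carries, after checking the eCRF completion guidelines.

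The cost is a few sentences and some extra programming to compare grades at each period's first dose. The documents do not show that an event identifier links related records. Where none exists, AEs of the same preferred term that cross the boundary need manual review. Data collection and participant management do not change.
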